**NCT04268745**

**ANALYSIS PLAN**

**May 6th, 2021**

The **specific aims** of this pilot project are:

**Aim #1:** Determine the extent to which sensory integration strategies differ between individuals with unilateral vestibular hypofunction and age-matched peers. Participants' head sway will be recorded as they experience two levels of moving stars and white noise, while standing on the floor or a compliant surface. Our working hypothesis is that patients with vestibular hypofunction utilize substitution strategies such that they will demonstrate greater visual and auditory reliance compared with controls, particularly when somatosensory cues are reduced via the support surface. We will then explore whether these mechanism changes after training.

**Aim #2:** Develop the protocol and establish the feasibility of a randomized controlled trial (RCT) comparing C.S.I. training to standard vestibular rehabilitation. Following the assessment, the patients will be randomized into standard vestibular rehabilitation vs. C.S.I. training. This pilot study will enable us to test the feasibility of our recruitment, randomization procedures, establish attrition rate, and test the training protocol.

**Aim #3:** Generate pilot data for sample size calculation for a properly powered RCT. The follow up RCT will test the effect of C.S.I. training on: Visual Vertigo Analog Scale (VVAS), Functional Gait Analysis (primary); balance confidence, overall disability (descriptive). In our preliminary study, 8 patients met the inclusion criteria for the current proposal. Following the C.S.I. training, they had a large effect size of 1.17 on the VVAS. The current study will allow us to identify the between-group effect size for the VVAS and for a functional gait outcome.

#### **Description of Outcome Measures:**

**FGA:** A functional test designed to assess individual's ability to perform various motor tasks, such as: walking with eyes closed, walking backwards, climbing stairs. There are 10 items, each is scored by a therapist on a scale of 0 (severe impairment) to 3 (normal). Intraclass correlation coefficients of .86 and .74 were found for interrater and intrarater reliability of the total FGA scores in vestibular disorders. Internal consistency was .79.

**VVAS:** The VVAS is a visual analog scale where a participant rates the intensity of their dizziness in 9 situations of visual motions that typically provoke dizziness. The VVAS is the second primary outcome measure because the intervention was designed to improve symptoms and function in sensory complex environments. Indeed, the VVAS has shown the largest changes from pre to post training changes in our preliminary work.

**ABC:** A subjective measure of confidence in performing activities without falling. Each item is scored from 0% (no confidence in one's balance) to 100% (full confidence in one's balance).

**DHI:** The DHI has 25 items involving the functional, emotional, and physical domains. Each item is scored as 'no', 'sometimes' or 'yes' to evaluate self-perceived disability imposed by dizziness.

**Head Root mean square velocity in the medio-lateral and anterior-posterior direction:** the difference in position between two consecutive data points divided by the average time interval. The velocity at each point is squared and summed. The square root of the sum is then divided by the number of data points.

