### Procedure

When a clinician identified a patient as eligible, they reviewed the informed consent and explained the study procedures. Following consent, patients underwent a baseline assessment including functional measures (Functional Gait Assessment [FGA], Timed-Up and Go [TUG], The Four-Square Step Test [FSST]), and self-reported questionnaires (Visual Vertigo Analog Scale [VVAS][27–29], Activities Specific Balance Confidence Scale [ABC], The Dizziness Handicap Inventory [DHI]). The assessment also included a postural control test using HMD. Standing hips-width apart on the floor, participants experienced two levels of visual surround and white noise while their head sway was recorded via the HTC Vive Pro headset. The total duration of the session was approximately 45 minutes. After the baseline assessment, the patients were randomized to 8 sessions of either traditional vestibular rehabilitation or C.S.I training followed by an immediate post assessment.

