#### **Data Analysis:**

**Aim 1:** For each of the measures of interest we will fit a linear mixed effects model to compare the age-matched controls to patients with vestibular hypofunction while accounting for the inherent multi-level study design (person, conditions, repetitions). The models will include main effects of group, visual condition, auditory condition, surface condition, as well as their interactions, while adjusting for age. *P*-values for the fixed effects will be calculated through the Satterthwaite approximation for the degrees of freedom for the T-distribution. We will repeat the analysis following the intervention, adjusting for group assignment and pre-intervention values. ABC and DHI will be used to describe the sample.

**Aim 2:** No statistical analysis needed.

**Aim 3:** First, following the intent-to-treat principle, a linear regression model will be fit with the VVAS and FGA as the primary dependent variable, on treatment group, controlling for baseline covariates (age and other self-reported questionnaire measures) to improve the precision of the treatment effect estimate, as well as pre-test scores. The potential efficacy of the intervention will be assessed based on a significant coefficient for treatment status. Second, as described above, we will fit a pattern mixture model to multiply impute any missing values, and use Rubin's rules to pool coefficients and their standard errors from the regression models fit to each imputed dataset. Data generated from this pilot randomized trial will be used to calculate the sample size needed for future, adequately powered, randomized controlled trials by estimating the difference in means for the treatment groups (i.e. a future expected effect size) as well as the variance of the primary outcomes and the values of other parameters necessary to compute the power function.

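### The SAP calls the Aim 1 sway outcome root mean square velocity, but the formula it writes out gives RMS divided by the square root of the number of samples

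*SAP*

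**What the plan says.** The SAP's Description of Outcome Measures names one sway measure: "Head Root mean square velocity in the medio-lateral and anterior-posterior direction". Velocity is defined as "the difference in position between two consecutive data points divided by the average time interval". The aggregation follows: "The velocity at each point is squared and summed. The square root of the sum is then divided by the number of data points". Neither document gives another formula.

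Aim 1 is the aim that uses head sway (SAP, specific aims): "Participants' head sway will be recorded as they experience two levels of moving stars". The Aim 1 mixed model is specified in the SAP's Data Analysis section: "The models will include main effects of group, visual condition, auditory condition, surface condition, as well as their interactions, while adjusting for age". A second fit comes after treatment: "We will repeat the analysis following the intervention, adjusting for group assignment and pre-intervention values". The SAP treats that later question as exploratory: "We will then explore whether these mechanism changes after training".

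The Protocol's Procedure section describes the recording only in this form: "participants experienced two levels of visual surround and white noise while their head sway was recorded via the HTC Vive Pro headset". Neither document states how long a recording lasts or the rate at which head position is sampled.

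**The concern.** The name and the recipe describe different quantities. An RMS divides the sum of squares by N and then takes the root. The SAP takes the root first and divides afterwards, so the divisor N is never under the root.

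Two things are at stake. First, anyone who follows the SAP literally reports numbers that are not velocities on their proper scale and cannot be set beside true RMS velocities. Second, a true RMS is normalised for the number of samples and the written quantity is not. A shorter recording of the same sway reads higher, so if N differed by group, condition or visit, that difference would enter the comparison.

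The SAP does not itemise its Aim 1 measures of interest, so it is an inference that this outcome is the one modelled. The inference is well supported: the Data Analysis section assigns ABC and DHI to describing the sample and VVAS and FGA to Aim 3, which leaves head velocity as the only defined outcome for Aim 1.

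**Working it through.** The plan gives no numerical value for this outcome, so there is no figure to reproduce. The check is algebra, followed by illustrations whose inputs are assumed.

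**1. The two formulas** (both from the SAP's outcome description)

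- By name: RMS = sqrt(sum(v²)/N) = sqrt(sum(v²))/sqrt(N)
- As written: W = sqrt(sum(v²))/N
- Therefore W = RMS/sqrt(N)

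**2. Two-point example, v = {3, 4}**

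- RMS = sqrt((9 + 16)/2) = sqrt(12.5) = 3.54
- W = sqrt(9 + 16)/2 = 5/2 = 2.50
- Ratio = 3.54/2.50 = 1.41 = sqrt(2)

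**3. Dependence on N.** Take a constant speed of 2, for which the RMS is 2 at every N. Then W = sqrt(4N)/N = 2/sqrt(N).

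| N (assumed) | RMS | W as written |
|---|---|---|
| 900 | 2.0 | 0.0667 |
| 1,800 | 2.0 | 0.0471 |
| 2,700 | 2.0 | 0.0385 |
| 5,400 | 2.0 | 0.0272 |

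**4. Scale error when N is constant.** The factor is sqrt(N): sqrt(1,000) = 32 and sqrt(10,000) = 100. At 90 samples per second for 60 seconds, N = 5,400 and the factor is 73.485. The 90 is the display refresh rate in the Protocol's System section, borrowed here as a sampling rate; the 60 seconds is assumed.

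**5. Effect on the models when N is constant.** Dividing the outcome by a constant divides every coefficient and its standard error by that constant, so t is unchanged. The exception is the slope on pre-intervention sway in the repeat model, where outcome and covariate shrink together. This takes the pre-intervention values to be the same sway measure. Simulated random-intercept fits with N = 5,400 and all inputs assumed agree:

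| Term | With true RMS | As written | Ratio | t (both) |
|---|---|---|---|---|
| Baseline model, group-by-visual | 0.19829 | 0.0026984 | 73.485 | 3.765 |
| Repeat model, treatment arm | -0.09873 | -0.0013435 | 73.485 | -2.554 |
| Repeat model, slope on pre-intervention sway | 0.5467 | 0.5467 | 1.000 | 27.289 |

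**6. If N varies (hypothetical).** For identical sway, a recording with a fraction f of the samples reads higher by 1/sqrt(f) - 1:

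- f = 0.95: 2.6%
- f = 0.90: 5.4%
- f = 0.75: 15.5%

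If every post-treatment recording were 10% shorter than its baseline recording, the slope on pre-intervention sway would be multiplied by 1/sqrt(0.90) = 1.054 (0.5467 becomes 0.5763 in the simulation). The arm coefficient would be off by 73.485 × sqrt(0.90) = 69.71 instead of 73.485. With N drawn at random between 80% and 100% of 5,400, the seven baseline-model coefficients checked were off by factors from 67.5 to 78.3, and the group-by-visual t moved from 3.765 to 3.311. Those last figures show that tests can move; they say nothing about how far they would move in this trial.

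**The case against.** The strongest reply is that this is an editorial slip with no demonstrated effect on any result. The name is a standard quantity, swapping the last two steps restores it, and an analyst working from the name would compute it correctly. With constant N no test changes. No cut-off or sample size rests on the absolute sway scale: the sample-size work in Aim 3 uses VVAS and FGA. Distorted tests need two conditions that the documents do not show: that the literal formula was coded, and that N differs materially between recordings. The Protocol calls the post-assessment identical to the baseline one, and no text describes shortened recordings.

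Most of this stands. The slip is probably one of wording, and the varying-N figures are hypothetical. What does not follow is that the text can be left alone. It is the operative formula for the only sway outcome defined, and a literal reading changes every reported value by an unstated factor. Nor is constant N established: an identical assessment does not guarantee equal sample counts, and dividing by an average time interval is compatible with uneven sampling, though it does not prove it.

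A smaller objection is that n position samples yield n - 1 velocities, so the exact ratio is n/sqrt(n - 1). At n = 5,400 that is 73.49 against 73.485, a difference of about 0.01%, which is negligible.

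**Conclusion.** The concern holds. The definition contradicts the name of the measure and gives RMS/sqrt(N). That rests on algebra alone and is certain; the consequences are conditional.

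- If the code uses the standard formula, only the SAP text is wrong.
- If the code follows the text and N is constant, sway values and the group, condition, interaction and age coefficients are too small by sqrt(N). Inference is untouched.
- If the code follows the text and N varies, no single factor repairs the results, and test statistics can move in a direction that the documents do not allow one to predict.

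The point should be fixed because the error is definite and the remedy costs almost nothing. There is no evidence that any conclusion would change.

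**What to change.** Replace the last two sentences of the definition with: *The velocities are squared and averaged over the N velocity values, and the square root of that mean is taken: RMS = sqrt(sum(v²)/N).* State the recording length and the head-tracking sampling rate beside it.

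Then confirm that the analysis code uses this formula. Only if values were produced with the written one, multiply each by the sqrt(N) of its own recording and refit the Aim 1 models.

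The cost is two sentences in the SAP, the two recording details, and a check of one line of code. No new data are needed, and nothing has to be recomputed if the code is already right.

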#### **Data Analysis:**

**Aim 1:** For each of the measures of interest we will fit a linear mixed effects model to compare the age-matched controls to patients with vestibular hypofunction while accounting for the inherent multi-level study design (person, conditions, repetitions). The models will include main effects of group, visual condition, auditory condition, surface condition, as well as their interactions, while adjusting for age. *P*-values for the fixed effects will be calculated through the Satterthwaite approximation for the degrees of freedom for the T-distribution. We will repeat the analysis following the intervention, adjusting for group assignment and pre-intervention values. ABC and DHI will be used to describe the sample.

**Aim 2:** No statistical analysis needed.

**Aim 3:** First, following the intent-to-treat principle, a linear regression model will be fit with the VVAS and FGA as the primary dependent variable, on treatment group, controlling for baseline covariates (age and other self-reported questionnaire measures) to improve the precision of the treatment effect estimate, as well as pre-test scores. The potential efficacy of the intervention will be assessed based on a significant coefficient for treatment status. Second, as described above, we will fit a pattern mixture model to multiply impute any missing values, and use Rubin's rules to pool coefficients and their standard errors from the regression models fit to each imputed dataset. Data generated from this pilot randomized trial will be used to calculate the sample size needed for future, adequately powered, randomized controlled trials by estimating the difference in means for the treatment groups (i.e. a future expected effect size) as well as the variance of the primary outcomes and the values of other parameters necessary to compute the power function.

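### Aim 3 judges potential efficacy by significance in a pilot and sizes the next RCT on the pilot's own estimated difference, with no stated way for its uncertainty to enter

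*SAP*

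**What the plan says.** Aim 3 in the SAP's Data Analysis section fits a linear regression of VVAS and FGA on treatment group, adjusted for pre-test score, age and other questionnaire measures. Its criterion is: "The potential efficacy of the intervention will be assessed based on a significant coefficient for treatment status". Missing values are multiply imputed, and Rubin's rules are used to "pool coefficients and their standard errors from the regression models fit to each imputed dataset".

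The future RCT is then to be sized "by estimating the difference in means for the treatment groups (i.e. a future expected effect size". The same sentence goes on to list the remaining inputs to the calculation, namely the outcome variance and whatever else the power function needs; it does not mention a standard error or confidence interval of the difference.

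Aim #3 in the list of specific aims gives the same intent: "The current study will allow us to identify the between-group effect size for the VVAS and for a functional gait outcome". It also places testing in the later trial: the sentence that names VVAS and FGA as primary opens with "The follow up RCT will test the effect of C.S.I. training on". The only numerical effect size comes from eight patients in preliminary work: "Following the C.S.I. training, they had a large effect size of 1.17 on the VVAS". No comparison group is described for it.

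**The concern.** Two uses of the pilot estimate ask more of it than a small sample can give.

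- **Significance as the criterion.** With no alpha, pilot size or power stated, the reader cannot tell how often a worthwhile effect would fail the test. In a small pilot, non-significance is a likely result even when the treatment works.
- **The point estimate as the planning effect.** The regression and pooling steps produce a standard error for the treatment difference, but the sizing sentence does not call on it. The variance that the sentence does name is the spread of the outcome between patients, which is a different quantity.

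Aim 3 exists to support a properly powered RCT, so the sizing rule is its main product. Required n varies with the inverse square of the effect, so a noisy effect estimate gives a much noisier n.

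**Working it through.** The documents contain no sample size calculation, so there is no figure to reproduce. What follows shows the size of the problem under assumed inputs.

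**Inputs from the documents.** Two arms with equal allocation (protocol, Randomization and Group Allocation); two primary outcomes; baseline-adjusted linear regression (SAP, Aim 3).

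**Assumed inputs.** 15 or 30 per arm; true standardised difference d = 0.5; pre-post correlation r = 0, 0.5 or 0.7; one pre-test covariate; two-sided 0.05; 80% power for the later RCT. Attrition and imputation are not modelled.

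**Needed n per arm** = 2 × ((1.96 + 0.842) × √(1 − r²) / d)². At d = 0.5 this is 62.8, 47.1 and 32.0 for r = 0, 0.5 and 0.7.

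**Precision of the pilot difference**, in SD units, is roughly √(2/n) × √(1 − r²). At r = 0.5 this is 0.365 × 0.866 = 0.32 with 15 per arm and 0.258 × 0.866 = 0.22 with 30 per arm, against a true effect of 0.5.

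**Simulation**, 400,000 pilots per setting, RCT sized on the baseline-adjusted residual SD:

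| r | n per arm | Significant, right direction | Estimate not positive | n within 25% of needed | RCT power under 50%, given a positive estimate |
|---|---|---|---|---|---|
| 0 | 15 | 0.254 | 0.089 | 0.136 | 0.323 |
| 0 | 30 | 0.470 | 0.027 | 0.195 | 0.220 |
| 0.5 | 15 | 0.322 | 0.060 | 0.155 | 0.285 |
| 0.5 | 30 | 0.586 | 0.013 | 0.220 | 0.186 |
| 0.7 | 15 | 0.443 | 0.030 | 0.186 | 0.237 |
| 0.7 | 30 | 0.752 | 0.004 | 0.263 | 0.142 |

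At r = 0.5, where 47 per arm are needed, the 10th to 90th percentile of the estimated n among positive estimates is about 13 to 390 (15 per arm) or 18 to 232 (30 per arm).

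**Which SD.** The SAP names the variance of the outcomes, which reads most naturally as the raw outcome SD. If the RCT is sized on that and then analysed with baseline adjustment, n is within 25% of needed in about 14% to 23% of pilots. The under-50%-power share then runs from 1% to 32%; at r = 0.5 it is 19% (15 per arm) or 9% (30 per arm). The imprecision stays, but the underpowering is milder when r > 0 because the raw SD overstates what an adjusted analysis needs.

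**Sensitivity, residual SD.**

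- d = 0.3: significant in 12% to 35%; n within 25% in 8% to 16%.
- d = 0.8: significant in 55% to 99%; n within 25% in 21% to 39%.
- Four covariates, d = 0.5: significant in 23% to 73%; n within 25% in 13% to 26%.

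**One pilot worked through** (20 per arm, observed d = 0.5, unadjusted). SE = √(2/20 + 0.25/80) = 0.32, so the 95% CI is −0.13 to 1.13. Required n per arm is 63 at the point estimate and 13 at the upper limit; at the lower limit no finite n exists.

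**The case against.** **The plan is modest.** It speaks of potential efficacy, calls itself a pilot and leaves testing to the follow-up RCT. A reader might infer that the pilot is meant to establish efficacy; the SAP does not say so. What stands is that even the modest judgement is tied to significance, which is the wrong instrument at this size.

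**Absence is shown only for the text at hand.** Some text was not available to this review, and Aim 3 refers back to an account of the pattern mixture model that the available text lacks. Alpha, pilot size or power may be stated elsewhere. The open reference to other parameters of the power function could also cover more. The claim is only that use of the standard error is not stated.

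**The later RCT will need its own sizing justification.** True, and no result of this trial changes. But the pilot is meant to supply the inputs for that justification.

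**Stronger readings that do not hold.**

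- *More than half of the resulting RCTs would be underpowered.* Sizing on the residual SD gives under 80% power in 51% to 56% of positive pilots, but any roughly median-unbiased estimate misses its target about half the time. On the raw SD with an adjusted RCT analysis, the range is 16% to 56%.
- *The RCT must be sized on a minimally important difference alone.* The documents give none for VVAS or FGA. If the chosen difference were 1.25 times the true effect, 78% to 94% of RCTs would have under 80% power, even with a cautious SD. That is a trade-off, not a correction.
- *The false-positive rate is 9.75%.* This is 1 − 0.95², and needs two independent outcomes with either one sufficing at 0.05. The SAP does not say whether one or both must be significant.
- *The RCT is sized only after a significant pilot, on an inflated effect.* The SAP sets no such condition.

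**Conclusion.** The point holds as a cheap improvement. As written, Aim 3 uses significance to judge potential efficacy and the pilot's point estimate as the planning effect, with no stated route for its uncertainty.

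Under the assumptions above at d = 0.5:

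- a real effect is missed in roughly 25% to 75% of pilots, so a non-significant result says little;
- the estimated n is within 25% of the needed n in about 14% to 26% of pilots, whichever SD is used;
- among positive estimates, RCT power is under 50% in about 14% to 32% (residual SD) or 1% to 32% (raw SD, adjusted RCT analysis).

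These are ranges over assumed values, not corrections of a stated figure. A large true effect with 30 per arm would make the pilot's test perform well, but at d = 0.8 the estimated n is still within 25% in at most 39%. The effect of 1.17 in eight patients does not settle which case applies, since it is not described as a between-group effect.

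**What to change.** **(a) Efficacy sentence.** Replace it with: *The adjusted between-group difference and its 95% CI will be reported for VVAS and FGA; the pilot will not be used to conclude efficacy or its absence.* If a test is kept, state alpha and whether one or both outcomes must be significant.

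**(b) Sizing sentence.** Amend it so that the point estimate is not the only effect-size input, for example: *The required n will be reported over the 95% CI of the adjusted difference, stating where no finite n exists. The SD used (baseline-adjusted residual or raw outcome) will be named and taken at its upper one-sided 80% confidence limit.* If an important difference for VVAS or FGA can be justified in advance, show its n alongside.

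The SD limit is the estimate times √(df / χ²₀.₂), where χ²₀.₂ is the 20th percentile on df = 2n − 2 − covariates. For the residual SD with one to five covariates, the factor is 1.142 to 1.157 at 15 per arm (df 27 to 23) and 1.091 to 1.095 at 30 per arm (df 57 to 53).

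**Cost.** Wording only. The pilot claims less. The SD limit multiplies the median n for a given difference by 1.27 to 1.30 at 15 per arm and by about 1.18 at 30 per arm. A range of n does not choose one; the RCT team must still justify its choice.
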